### Power Calculation for Predictive Modeling

The goal here is to determine whether there is a significant difference between the clinical benefits of patients in different marker strata. That is, we are testing the interaction of the dichotomized marker value (we discuss how to dichotomize the marker value in details in our analysis plan in the following section) and the treatment group. We calculate our power based on the method by Peterson and George.

We denote the hazard function for each patient subgroup as the following:

	Marker stratum 1	Marker stratum 2
HDI	$\lambda_{11} = \lambda(t)$	$\lambda_{12} = \lambda(t)\lambda_{\text{Marker}}(t)$
Ipilimumab	$\lambda_{21} = \lambda(t)\lambda_{\text{Ipi}}(t)$	$\lambda_{22} = \lambda_{\text{Ipi}}(t)\lambda_{\text{Marker}}(t)\lambda_{\text{Interaction}}(t)$

where

$\lambda(t)$  is the baseline hazard

$\lambda_{\text{Ipi}}(t)$  is the hazard for the Ipilimumab group

$\lambda_{\text{Marker}}(t)$  is the hazard for marker stratum2 and

$\lambda_{\text{Interaction}}(t)$  is the hazard for the treatment by marker stratum interaction.

Denote  $N$  the sample size,  $f_{ij}$ , the number of subjects in treatment group  $i$  and marker stratum  $j$ , and  $e_{ij}$ , the event probability in treatment group  $i$  and marker stratum  $j$ . Define that  $\Delta = \frac{\Delta_1}{\Delta_2} = \frac{\lambda_{11} / \lambda_{21}}{\lambda_{12} / \lambda_{22}}$ , then the power to test the null hypothesis of  $\Delta = 1$

can be calculated using the following formula:

$$\text{Power} = \Phi^{-1} \left( \sqrt{N(\log \Delta)^2 / \sum \frac{1}{e_{ij} f_{ij}}} - Z_{1-\alpha/2} \right)$$

- $\alpha = 0.01$  : we do not intend to validate more than 5 predictive markers (and/or panels) in the validation set, thus, our type I error is set at  $0.05/5=0.01$ . All tests will be two-sided.

- For the purpose of power calculation, we assume the RFS time follows an exponential distribution.
- N: 250 on the ipilimumab arm + 300 on the HDI arm. We expect that we will be able to obtain samples from approximately 80% of the subjects. We expect that the assay success rate is at least 95%. Thus N is estimated to be 418.
- $f_{ij}$ : since this is a randomized trial, we assumed that the marker distribution in the two arms are balanced. Thus we may estimate  $f_{ij} = t_i \times g_j$  where  $t_i$  and  $g_j$  are the frequencies of treatment  $i$  and marker stratum  $j$ . In our data,  $t_1 = 300/550$  and  $t_2 = 250/550$ , we calculate the power for  $g_i$  in the range of 50%-70%.
- $e_{ij}$ : with the exponential failure and uniformed accrual assumption,  $e_{ij}$  is calculated based the accrual rate, minimum follow up time and  $\lambda_{ij}$ . The accrual rate for E1609 is approximately 40/month, by the time of the analysis we will have at least 1 year of follow up for all the subjects.
- $\lambda_{ij}$ 's : determine the effect size  $\Delta$ . Although  $\lambda_{ij}$  (hazard rate for patients in treatment arm  $i$  marker stratum  $j$ , which is unknown. However, the hazard rate for treatment arm  $i$ ,  $\lambda_i$ , can be deduced from the E1609 protocol. It was assumed that the RFS function follow a curate model of the following form:  $D_A(t) = p + (1-p)\exp(-\beta t)$ , where  $p=0.29$ , and the median RFS for the uncured patients on HDI arm is assumed to be 0.487 year. Thus  $\beta = -\log(2)/0.487 = 1.423$ . Set  $D_A(t_{0.5}) = 0.5$ , we estimate that the median survival time for HDI group to be 0.756 year. For the purpose of power calculation, we use exponential distribution to approximate the RFS function in each treatment group. Thus,  $\lambda_1 = \log(2)/0.756 = 0.917$ . It was assumed that a HR of 0.75 will be observed between the ipilimumab arm and the HDI arm, thus,  $\lambda_2 = 0.75 \times \lambda_1 = 0.688$ . We further approximate  $\lambda_i = \sum_j g_j \times \lambda_{ij}$ .

The following table listed the power for different marker stratum 1 frequencies ( $g_1$ ), and different effect sizes. We only considered marker with qualitative interaction with the treatment, assuming that patients in marker stratum 1 benefit from the ipilimumab and those in marker will benefit from HDI. Thus, we consider the situations where  $\lambda_{11} > \lambda_{21}$  and  $\lambda_{12} < \lambda_{22}$  only. We set  $\lambda_{11}$  and  $\lambda_{21}$  within the range of 0.7-1.2. The SWOG webtool (<http://stattools.crab.org>) was used for the power calculation. Here we assume the accrual time is 40 months (Accrual=40/12=3.3), minimum follow up is 12 months (Follow=12/12=1), Cell Freq Treat1/Strat1=  $f_{11}$ , Cell Freq Treat1/Strat2=  $f_{12}$ , Cell Freq Treat2/Strat1=  $f_{21}$ , Cell Freq Treat2/Strat2=  $f_{22}$ , Hazard Rate Treat1/Strat1= $\lambda_{11}$ , Hazard Rate Treat1/Strat2= $\lambda_{12}$ , Haz Ratio T1/T2 STrat1= $\Delta_1$ , and Haz Ratio T1/T2 Strat2= $\Delta_2$ .

Table 1 Power calculation for test of interaction ( $\alpha = 0.01$ , two-sided)

Marker stratum I Freq. (g i )	$f_{10}$	$f_{12}$	$f_{13}$	$f_{17}$	$\lambda_{11}$	$\lambda_{12}$	$\lambda_{13}$	$\lambda_{17}$	$\Delta_1$	$\Delta_2$	$\Delta$	Power
0.5	0.273	0.273	0.227	0.227	1.1	0.734	0.6	0.776	1.833	0.946	1.938	0.69
					1	0.834	0.5	0.876	2	0.952	2.101	0.8
					1.15	0.684	0.6	0.776	1.917	0.881	2.174	0.84
					1.05	0.784	0.5	0.876	2.1	0.895	2.346	0.91
					1.15	0.684	0.55	0.826	2.091	0.828	2.525	0.95
0.6	0.327	0.218	0.273	0.182	1.2	0.634	0.5	0.876	2.4	0.724	3.316	1
					1.05	0.718	0.6	0.82	1.75	0.875	2	0.72
					1	0.793	0.55	0.895	1.818	0.885	2.053	0.76
					0.95	0.868	0.5	0.97	1.9	0.894	2.124	0.8
					1	0.793	0.5	0.97	2	0.817	2.448	0.93
0.7	0.382	0.164	0.318	0.136	1.1	0.643	0.5	0.97	2.2	0.662	3.321	1
					1	0.723	0.6	0.893	1.667	0.81	2.058	0.69
					1.2	0.257	0.8	0.427	1.5	0.602	2.494	0.79
					1	0.723	0.55	1.01	1.818	0.716	2.539	0.92
					1.15	0.373	0.7	0.66	1.643	0.566	2.904	0.95
					1.05	0.607	0.5	1.127	2.1	0.538	3.9	1

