9.4 First Step: Comparison of Low-dose Ipi vs. HDI

9.4.1 RFS

The recurrence-free survival (RFS) is defined from the time from randomization to the time of disease recurrence or death from any cause.

Since a moderate percentage of long-term cures have been observed in melanoma patients on previous melanoma study, E4697, we have used a model proposed by Berkson and Gage (1952) and Goldman (1984). This model specifies that the target population is a mixture, with proportion  $p$  who will be cured, and  $(1 - p)$  who will fail according to an exponential distribution with rate  $\beta$ . The RFS function  $D(t)$  for the HDI arm (A) and the Ipi arm (B) is expressed as:

$$D_A(t) = p + (1 - p) \exp(-\beta t)$$

$$D_B(t) = \{p + (1 - p) \exp(-\beta t)\}^\theta$$

where  $\theta$  represents a hazard ratio under the proportional hazards alternative. For RFS, it was assumed that the cure rate is 29% and the median survival time for those not cured is 0.487 years in patients randomized to the HDI arm. Under the proportional hazards alternative, we hypothesize that Ipi will reduce the hazard by 25% (hazard ratio  $\theta=0.75$ ). The full information is 655 events in high-dose Ipi and HDI groups. This design provides at least 80% power at a one-sided type I error rate of 0.003. An ITT analysis using the stratified log-rank test will be performed.

9.4.2 OS

Based on E4697 data, the cure rate model is appropriate for this endpoint. This model specifies that the target population is a mixture, with proportion  $p$  who will be cured, and  $(1 - p)$  who will fail according to an exponential distribution with rate  $\beta$ . The survival function  $S(t)$  for the HDI arm (A) and the Ipi arm (B) is expressed as:

$$S_A(t) = p + (1 - p) \exp(-\beta t)$$

$$S_B(t) = \{p + (1 - p) \exp(-\beta t)\}^\theta$$

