### **Power for Predictive Modeling**

With limited preliminary data, predictive modeling is our secondary objective. Nevertheless, here we estimate our power for validation of a predictive biomarker in the validation set. We base our calculation on the analysis of one of the ipilimumab arms (HIP or LIP) and the HDI arm. However, it is very likely that the RFS profiles are very similar between the two ipilimumab arms. If this turned out to be the case by the time we analyze the data, we will consider combining the data of these two arms. Thus, our power estimate here is a conservative estimate. The goal here is to determine whether there is a significant difference between the clinical benefits of patients in different marker strata. That is, we are testing the interaction of the dichotomized marker value (we discuss how to dichotomize the marker value in details in our analysis plan in the following section) and the treatment group. We calculate our power based on the method by Peterson and George. As shown in Table 1, with 418 samples total, we will be able to detect an interaction term with HR between 1.9-2.1 assuming the marker stratum 1 proportion is between 50-70% with a two-sided test ( $\alpha=0.01$ ). Details on the power calculation for the predictive modeling is given below.

Table 1 Power calculation for test of interaction ( $\alpha = 0.01$ , two-sided)

Marker stratum 1 Freq. ( $g_j$ )	$f_{11}$	$f_{12}$	$f_{21}$	$f_{22}$	$\lambda_{11}$	$\lambda_{12}$	$\lambda_{21}$	$\lambda_{22}$	$\Delta_1$	$\Delta_2$	$\Delta$	Power
0.5	0.273	0.273	0.227	0.227	1.1	0.734	0.6	0.776	1.833	0.946	1.938	0.69
					1	0.834	0.5	0.876	2	0.952	2.101	0.8
					1.15	0.684	0.6	0.776	1.917	0.881	2.174	0.84
					1.05	0.784	0.5	0.876	2.1	0.895	2.346	0.91
					1.15	0.684	0.55	0.826	2.091	0.828	2.525	0.95
					1.2	0.634	0.5	0.876	2.4	0.724	3.316	1
0.6	0.327	0.218	0.273	0.182	1.05	0.718	0.6	0.82	1.75	0.875	2	0.72
					1	0.793	0.55	0.895	1.818	0.885	2.053	0.76
					0.95	0.868	0.5	0.97	1.9	0.894	2.124	0.8
					1	0.793	0.5	0.97	2	0.817	2.448	0.93
					1.1	0.643	0.5	0.97	2.2	0.662	3.321	1
					1	0.723	0.6	0.893	1.667	0.81	2.058	0.69
0.7	0.382	0.164	0.318	0.136	1.2	0.257	0.8	0.427	1.5	0.602	2.494	0.79
					1	0.723	0.55	1.01	1.818	0.716	2.539	0.92
					1.15	0.373	0.7	0.66	1.643	0.566	2.904	0.95
					1.05	0.607	0.5	1.127	2.1	0.538	3.9	1

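### Appendix XIX predictive-marker power rests on a wrong median and ignores the 29% cure fraction: the rows tabled at 0.80 have power of about 0.63

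*Combined protocol and SAP*

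**What the plan says.** Section 9.4.1 gives the RFS design model for the HDI arm: "it was assumed that the cure rate is 29% and the median survival time for those not cured is 0.487 years". The hazard ratio for ipilimumab is 0.75.

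Appendix XIX, Power Calculation for Predictive Modeling, starts from the same model ("the median RFS for the uncured patients on HDI arm is assumed to be 0.487 year", cure proportion 0.29, rate 1.423). It sets the survival function to 0.5 and reports: "we estimate that the median survival time for HDI group to be 0.756 year". It then drops the cure model: "For the purpose of power calculation, we assume the RFS time follows an exponential distribution", and again, "we use exponential distribution to approximate the RFS function in each treatment group". From this come hazards of 0.917 for HDI and 0.688 for ipilimumab, and the cell hazards in Table 1 are chosen to average to them.

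The sample is the validation half, "N: 250 on the ipilimumab arm + 300 on the HDI arm", reduced to 418 by 80% specimen availability and 95% assay success. The test is two-sided at 0.01, with 40 months of accrual and at least 12 months of follow-up.

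The text in XIX.8 (Power for Predictive Modeling) summarises Table 1 as follows: "we will be able to detect an interaction term with HR between 1.9-2.1 assuming the marker stratum 1 proportion is between 50-70" percent. It also describes the estimate as conservative, because the two ipilimumab arms may later be combined.

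**The concern.** There are three separate faults.

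1. The median does not solve the appendix's own equation, and the error passes into both arm hazards and so into the cell hazards of Table 1.
2. The power formula depends on the probability of an event in each cell. An exponential curve matched at the median has no plateau, so nearly every patient eventually fails. Under the protocol's model no more than 71% of HDI patients can ever fail.
3. The range 1.9 to 2.1 is described as detectable at stratum frequencies of 50 to 70%, yet Table 1 as printed gives power 0.69 at 1.938 (50%) and 0.69 at 2.058 (70%).

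Half of the sample is held back for one validation test per marker at 0.01. If true power is near 0.63, more than one in three real interactions of ratio 2.1 would be missed, where the rows tabled at 0.80 imply one in five. A null result could be over-read as absence of a predictive marker.

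**Working it through.** **Inputs.** Cure proportion 0.29 and uncured median 0.487 years (section 9.4.1 and Appendix XIX); hazard ratio 0.75; N = 550 × 0.80 × 0.95 = 418; arm shares 300/550 and 250/550; two-sided alpha 0.01 (z = 2.576); accrual A = 40/12 years; minimum follow-up 1 year; cell hazards from Table 1.

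**Median.** Rate = ln 2 / 0.487 = 1.423. Solving 0.29 + 0.71·exp(−1.423t) = 0.5 gives t = −ln(0.21/0.71)/1.423 = 0.856 years. At t = 0.756 the function is 0.532, not 0.5. The hazards should therefore be ln 2/0.856 = 0.810 and 0.75 × 0.810 = 0.607, instead of 0.917 and 0.688.

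**Power formula.** Power = Φ(√[N(ln Δ)² / Σ 1/(e_ij f_ij)] − 2.576), where f_ij are the cell shares and e_ij the event probabilities. The appendix prints Φ⁻¹ where Φ is meant, and gives the rate with a stray minus sign. Neither slip affects the table.

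**Reproducing the plan.** Under the exponential with uniform accrual, e = 1 − [exp(−λ) − exp(−λ(A+1))]/(λA). For the 50% row with hazards 1, 0.834, 0.5 and 0.876 (Δ = 2.101):

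- e = 0.894, 0.853, 0.705, 0.865
- Σ 1/(e f) = 19.73
- N(ln Δ)² = 418 × 0.551 = 230.3
- √(230.3/19.73) − 2.576 = 0.84, so power is 0.80, as tabled

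All 16 rows of Table 1 reproduce to within 0.01.

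**Same row under the protocol's RFS model.** Each cell's survival is D(t)^(λ_ij/0.917), with D(t) = 0.29 + 0.71·exp(−1.423t), averaged over follow-up from 1 to 4.33 years. Δ is unchanged.

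- e = 0.706, 0.640, 0.459, 0.658
- Σ 1/(e f) = 27.21
- √(230.3/27.21) − 2.576 = 0.33, so power is 0.63

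A Cox simulation of this row (600 replicates) gave 0.64. Expected events in the row fall from 348 to 259, a ratio of 1.34. Average event probabilities (HDI/ipilimumab) are 0.875/0.803 under the exponential and 0.674/0.570 under the cure model.

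| Stratum 1 | Δ | Table 1 | Reproduced | Median corrected, exponential kept | Cure model |
|---|---|---|---|---|---|
| 50% | 1.938 | 0.69 | 0.69 | 0.66 | 0.52 |
| 50% | 2.101 | 0.80 | 0.80 | 0.78 | 0.63 |
| 50% | 2.346 | 0.91 | 0.91 | 0.90 | 0.78 |
| 60% | 2.124 | 0.80 | 0.80 | 0.78 | 0.64 |
| 70% | 2.058 | 0.69 | 0.69 | 0.67 | 0.53 |
| 70% | 2.494 | 0.79 | 0.79 | 0.76 | 0.54 |

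**Ratio needed for 80% power.** With 2.576 + 0.842 = 3.417 after rounding, Δ = exp(3.417·√(Σ/418)). For the 50% row, exp(3.417·√(27.21/418)) = 2.39. For the 60% row, Σ = 27.36 gives 2.40. For the 70% row at 2.058, Σ = 31.18 gives 2.54. Rows with a very low hazard in stratum 2 need more: the 70% row at 2.494 has Σ = 48.97, which gives 3.2. Keeping Δ at 2.10 would need N of about 577.

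**Sensitivity of the two 0.80 rows (one ipilimumab arm).** Taking the tabled hazards relative to 0.810 instead of 0.917 gives 0.67 and 0.68. Unlimited follow-up gives 0.66 and 0.67. Both together give 0.70 and 0.71. Multiplying the exponential e_ij by 0.71 gives about 0.62.

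**The case against.** The best counter-argument is the pooling clause. The appendix computes power for one ipilimumab arm and says the two may be combined if their RFS profiles are similar. With 300 HDI and 500 pooled ipilimumab patients, N = 800 × 0.80 × 0.95 = 608. Cure-model power is then 0.82 for both rows tabled at 0.80, but only 0.68 for the 70% row at 2.494. This is a real mitigation. It is conditional, however, and it does not make the printed single-arm figures at N = 418 correct or conservative.

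Second, the exponential is openly declared, so most of the shortfall comes from a modelling choice and only about 2 points from the arithmetic error. That is true. But disclosure does not make the approximation adequate: the appendix derives its hazard from the cure model and then discards the feature that limits events. The same appendix plans supplementary cure-rate analyses because long-term cures have been observed.

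Third, the sentence on 1.9 to 2.1 names no power level, and the 0.69 values are printed beside it. The fault there is loose wording more than contradiction, though a reader will normally take a detectable ratio to mean conventional power.

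Finally, the objective is secondary, preliminary data are acknowledged to be limited, the validation step also compares direction and size of effect, and nothing in the appendix says that a null result will be read as absence of a predictive marker. This limits the consequence but leaves the stated power wrong.

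**Conclusion.** The concern holds. The median of 0.756 years is an error on any reading; the correct value is 0.856. Under the trial's own RFS model, the two rows tabled at 0.80 have power of about 0.63 and 0.64, and the 70% row at 2.494 about 0.54 instead of 0.79. Across the ratios the text calls detectable, power is about 0.52 to 0.64.

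These figures assume the protocol's 29% cure rate and proportional hazards, the appendix's accrual and follow-up, one ipilimumab arm, and tabled hazards read relative to 0.917. The most favourable single-arm variant examined reaches 0.71; only pooling the ipilimumab arms brings those two rows back to about 0.82. The effect is confined to a secondary correlative objective. The RFS and OS comparisons in sections 9.4 and 9.5 do not use this calculation.

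**What to change.** In Appendix XIX, Power Calculation for Predictive Modeling:

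- Replace 0.756 by 0.856 years, and the arm hazards 0.917 and 0.688 by 0.810 and 0.607.
- Compute e_ij from the section 9.4.1 cure model averaged over follow-up of 1 to 4.33 years, and regenerate both printings of Table 1. Correct the Φ⁻¹ and the minus sign at the same time.
- In XIX.8, replace the range 1.9 to 2.1 by the ratio that gives 80% power at alpha 0.01 with one ipilimumab arm: about 2.4 at stratum frequencies of 50 to 60% and about 2.55 at 70%. Add that a low-hazard stratum needs a larger ratio.
- Remove the description of the single-arm estimate as conservative. If pooling remains an option, add separate rows for N = 608 and state the condition for pooling.

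The cost is a few sentences and one recalculated table, and the stated detectable effect becomes less favourable. No change to sample size, conduct or the primary analysis is needed.
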